## PROJECT TITLE AND NARRATIVE

### Goal-Directed Resilience Training to Mitigate Chronic Pain in Former Football Players

How can former football players overcome the physical pain that commonly results from years of intense training and performance? This pilot study seeks to test the efficacy of a resilience skills training intervention for former football players who experience chronic pain. Chronic pain threatens quality of life, and the culture of elite athletes is poorly adapted to the chronic condition of pain. Innovative strategies that are both culturally acceptable and effective are needed to address the needs of players who may have a reluctance to engage traditional treatment approaches.

## PROJECT ABSTRACT

Our overarching goal is to strengthen the capacity for former football players to maintain adaptive engagement in valued activities despite chronic pain. Responding to recent findings from the Harvard Football Player Health Study (HFPHS) that identified pain as a significant challenge, we propose a pilot study that tests a resilience skills training intervention with former football players who currently experience chronic pain. Our proposed study builds on previous work conducted at Morehouse School of Medicine engaging retired NFL players and ongoing resilience intervention research involving veteran and community-based populations. Specifically, we plan to test a novel Goal Directed Resilience Training (GRIT) in a subsample of Atlanta-based former players who have chronic pain and would benefit from resilience training. This pilot study has the potential to advance strategies to improve the wellbeing and functional status of former players impacted by pain.

## OVERVIEW AND BACKGROUND

1. Chronic pain is a national medical problem and priority as evidenced by the massive opioid epidemic. For former professional football players, chronic pain can be the dominant condition of life, degrading its quality in multiple domains. We propose to address chronic pain with a resilience skills training intervention to improve functions affected by pain, i.e., quality of life, personal relationships, and personal growth or development. The specific aim of this study is to test an intervention to decrease chronic pain and comorbid symptoms and improve a broader adaptive level of functioning through Goal-Directed Resilience Training (GRIT) for chronic pain. We hypothesize:
  - a. GRIT training intervention versus control training will be associated with reduced chronic pain and related symptoms of insomnia, anxiety, depression, improved emotional functions, and improved neurocognitive functions.
  - b. Improved self-reported physical health, quality of life, personal relationships, and personal growth will be evident for intervention versus control participants.

Although the body as internal environment is long recognized as such (*milieu intérieur* of Claude Bernard, 1865 in Gross 1998; interoception, Craig, 2009), our approach is innovative in treating pain as an internal interoceptive environment, one that is characterized by unpredictability and aversiveness. These two qualities also define extreme environments, be these extremes of weather or prisoner of war camps. Resilience, if thought of as a process as well as a state, buffers against the harshness of the environment, facilitating success and thriving in the midst of adversity. The engine that drives, maintains, and increases pain is unpredictability. The unpredictability of pain (in terms of intensity, timing, duration, physical and social context, etc.) makes it a powerful, variable, and often unstoppable force. We propose an interactive model of Environment x Biobehavioral Control in which chronic pain and resistance or resilience to pain are embedded. We believe this model explains the preliminary successes and points to the promise of our GRIT intervention.

Scientific Justification. Reciprocating dichotomies are described in a variety of neuroscience approaches, such as the predictive and reactive control systems (PARCS) of Tops (Tops, Luu, Boksem, & Tucker, 2014), voluntary and stimulus-driven actions (Hughes, Schütz-Bosbach, & Waszak, 2011), and others. The underlying dichotomy is fight-flight or stimulus-driven responding (e.g. a tiger jumping through the door of your room, you respond to the threat with fight-flight) and goal-directed responding (e.g. taking notes during a lecture which would be incompatible with saving

your life while the tiger is jumping through the door of the lecture hall). The particular contribution of our model is that it goes beyond dichotomies and considers all possible combinations in an interactive model of Environment x Biobehavioral control (ExBC). This model recognizes that goal-directed responding occurs not only in safe environments (e.g. taking notes during a lecture) but also in unpredictable environments (you dive under a table to avoid the tiger scene and continue note taking – real dedication here!) and that goal-direction can stop threat and pain. This capacity for goal-direction led to the development of Goal-Directed Resilience in Training (GRIT) for chronic pain.

Preliminary Activities. In 2010, Morehouse School of Medicine (MSM) hosted community huddles in 15 cities nationwide over 18 months and included private discussions with former NFL players and their families and community town-hall forums. We engaged nearly 400 former players and family members and nearly 1,800 community stakeholders to raise awareness about sports-related head injuries, dementia, depression, and other mental illnesses, developing trust within this community. Approaches that emphasize the development of strengths and capacities beyond the treatment of symptoms are culturally acceptable to former players.

The proposed GRIT intervention has been applied to pain and PTSD in veteran and civilian populations (Kent, Rivers, & Wrenn, 2015; Kent, Davis, Stark, & Stewart 2011). The unpredictability of the pain body environment evokes automatic **stimulus-driven responses** that displace and inhibit **goal-directed responses**. Through re-experience, GRIT trains goal-direction as a natural incompatible response to chronic pain. It consists of taking goal-directed responding from the predictable safe environment into dysfunction and pathology and thus transforming dysfunction into resilience. This approach can be applied to other unpredictable aversive environments: unpredictable aversive cultural experience (minority/marginalized social position), interpersonal stress (divorce), discrimination in health care that exacerbate and help maintain pain. The GRIT simulation process is indicated by the arrow in Figure 1.

Biobehavioral Control	Unpredictable Environment	Predictable Environment
Stimulus-Guided Response (Reactive)	
1. ACUTE THREAT, not safe Threat can be stopped through fight/flight.
 
ADAPTIVE REACTIVITY TO RESTORE HOMEOSTASIS Responses are fast, here-and-now Learning is fast, one-trial Focus is narrow on threat
	
2. MALADAPTIVE REACTIVITY IN CHRONIC CONDITIONS, not safe Symptoms cannot be easily stopped; are maintained by unpredictability.
 
DYSFUNCTION Person declines - pathology
 
Goal-Directed Response (Predictive)	
4. CHRONIC or ACUTE, not safe Symptoms can be stopped through goal-direction and social relatedness
 
RESILIENCE Person grows - eudaimonia
	
3. PREDICTABLE, safe
 
DEVELOPMENT & GROWTH Goal-directed Future oriented Learning is slow Slow development of skills & projects Building models, simulating for prediction
 
Engagement & social relatedness from everyday life (e.g. childhood or early adulthood)
 

**Figure 1.** Environment x Biobehavioral Control Model

## PROJECT DETAILS

### Experimental Design and Methods

#### Intervention Training for Former Players

Between 20 to 48 eligible and consented participants from the Atlanta area will be identified (with a goal of 40 completing the study). They will undergo a pre-training test session and will then be randomized to either the Immediate GRIT (ImT) training intervention or the Delayed Training (DeT) control. At this time there will be one intervention immediate (ImT) group and one delayed (DeT) control group of 5-12 participants per group. The immediate (ImT) group will be trained for 4 weeks with 2 biweekly sessions. At the end of GRIT training they will be post-tested. The delayed (DeT) group wait during these 4 weeks and do not receive training. At the end of the 4-week waiting period, they will also be post-tested. At this point, they will be offered GRIT training for 4 weeks with 2 biweekly sessions. At the end of their training, they will be given a second post-testing. This process will then be repeated for two additional groups of 5-12 ImT and 5-12 DeT participants.

Goal-Directed Resilience Training (GRIT) is a hands-on experiential simulation and repeated practice that takes the person back to his/her earlier goal-directed experiences and then applies them to episodes of pain and suffering. The brain is inherently a simulation device where actual and simulated actions activate the same cortical areas (e.g. Decety & Grèzes, 2006). Goal-directed responding is inhibited by stimulus-guided responses to fear or pain. The restoration of goal-directed engagement and relatedness are natural capacities we have for pain control (Erpelding & Davis, 2013). This is the main focus of the training. Participants are asked to identify engagement and social relatedness (the goal-directed resources) from childhood or early adulthood, since these early years are formative, as well as examples from present time. They are asked to re-experience these in descriptions and sensations, then take these episodes into experiences of pain or trauma, thereby transforming these into resilience. This is accomplished through a manualized program consisting of four modules: engagement, social relatedness, transformation, and defining a good life. GRIT training is a small-group intervention consisting of 5-12 participants per group. We propose a pilot study of 20-48 participants or 4 groups with 2 intervention and 2 control conditions to be conducted in Atlanta. Up to eight (8) subjects beyond our goal of 40 will be added to make up for attrition. Individuals randomized to control condition will participate in the GRIT the training after post-assessment. Training extends over 4 weeks, consists of 90-minute biweekly visits, for a total of 8 visits.

**Outcome Measures.** To test hypotheses 1 and 2, outcome measures for GRIT training include focused pain-relevant symptom measures, adaptive functions measures, neurocognitive measures, and PACE, as listed in Table 2. List of outcome measures are provided in Appendix 1.

Table 2. Proposed Outcome Measures for GRIT Training

Focused Pain-Relevant Measures	
Pain Outcome Questionnaire (POQ), (20 items)	
PROMIS Pain Interference Short Form. (8 items)	
PROMIS Sleep Impairment (8 items)	
PROMIS Sleep Disturbance (8 items)	
Pain Catastrophizing Scale, (13 items)	
Chronic Pain Acceptance Questionnaire, (8 items)	[time to completion = 23 minutes]
Adaptive Functions Measures	
Physical Health: SF-36 Health Measure: physical & mental health, (36 items)	
Well-Being: Ryff 's Positive Relations & Personal Growth, (14 items)	
Perceived Stress Scale (10 items)	

HEMA: Hedonic and Eudaimonic Motives for Activities, (9 items)  
PACE – Predictability as Core Evaluation [as outcome measure], (47 items)

Emotional Symptoms:

PHQ-9: Patient Health Questionnaire Depression Scale, (9 items)

GAD-7: Generalized Anxiety Disorder Scale, (7 items)

ACE: Adverse Childhood Experience, (10 items)

[time to completion = 50 minutes]

**Neurocognitive Functions**

D-KEFS: Delis-Kaplan Executive Function: Verbal Fluency, Color-Word Interference

RBANS: Repeatable Battery for the Assessment of Neuropsychological Status

NAB: Neuropsychological Assessment Battery: Word Generation [time to completion = 30 minutes]

**Preventing Chronic Pain Strategy**

PACE: Predictability as Core Evaluation, for chronic pain (used here as pre-post outcome measure)

**Physical Functions Measure** e.g. pre-post time measure of walking

Total time required to complete questionnaire scales and neurocognitive tests is 90 to 120 minutes.

**Subjects**

Between 20-48 former NFL players will be recruited for participation. The inclusion/exclusion criteria are listed in Table 3 below.

Table 3. Inclusion/Exclusion Criteria

Inclusion criteria	Exclusion criteria
Former football player between 18 – 65 of age who have passed pre-selection and are referred by FPHS, potentially diverse racial & ethnic identities	1. Active suicidality or suicidal intent requiring greater than outpatient level of care (Columbia Suicide Severity Rating Scale – C-SSRS)* 2. High risk drinking of alcohol (based on scoring guidelines of AUDIT-C)* 3. Active psychosis (Psychosis Screener)* 4. Inability to participate in a small group setting (self-reported inability to regulate constructive social interaction in small group setting)* 5. Inability to meet projected attendance requirements.**

\* Eligibility screening tools are provided in Appendices 2 and 3; Mental health action required for further evaluation and possible treatment are outlined in Appendix 8.

\*\* Attendance requirements are as follows. Participants are allowed to miss 2 out of 8 sessions. They are also given the option to make up one or both sessions. They are allowed to make up a maximum of 2 sessions. If they miss a 3rd session, they are not allowed to make it up but can stay in the study. If they miss a 4th session, they will be terminated from the study.

**Statistical Considerations**

Design. This is a balanced randomized block design. Twenty (20) to forty-eight (48) eligible and consenting participants from the Atlanta area will be identified from the cohort of research participants at the Football Players Health Study (FPHS) at Harvard University in Boston, MA. They will be selected based on answers previously given to specific FPHS survey questions listed below. They will undergo a pre-training test session and consequently be randomized with 1:1 allocation to either the Immediate GRIT training (ImT) intervention group or the Delayed (DeT) training control group. There will be two Immediate (ImT) intervention groups of 5-12 participants per training group and two Delayed training (DeT) control groups with 5-12 participants in each control group.

Outcome measures (c.f. Table 2). Sample Size and Power. This is a pilot study. Using focused pain-relevant or adaptive measures as outcomes with effect size (minimally detectable differences in weighted scores between the ImT experimental and DeT control group, scaled by pooled standard deviation) of 1, 2, 3, and 4, a regression model with treatment, age and block as effects and an overall 0.05 significance level, 20 participants per group yields an 0.80 statistical power.

For all analyses intent-to-treat principles will be adopted for those who drop out. Pre-treatment scores will be used to generate sampling frames consistent with a multiple imputation approach (Rubin, 1999) to determine post-treatment values.

Statistical Analyses. Summaries will rely on means, standard deviations for continuous variables and frequency and percentages for categorical ones. Univariate analyses for weighted scores and continuous variables groups comparisons will rely on t-tests (if normality assumptions are upheld) and/or non-parametric testing. Categorical variables will be compared using Chi-square/Fisher exact/McNamer testing. Multivariate analyses for the responses of scales/subscales weighted scores, factoring in covariates effects on interventions vs. control, age, block, pre-treatment scores, will use the Generalized Linear Mixed Modeling (GLMM) approach that will allow blocks as random effects and grant each subject their own intercept. All analyses will be conducted using SAS version 9.4

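### No primary outcome, success rule or multiplicity adjustment is named, so the *overall* 0.05 level is undefined across 13–14 measures, and the single 0.80 power does not match the listed effects

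*Combined protocol and SAP*

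**What the plan says.** The power statement is in Statistical Considerations, under Sample Size and Power. Its outcomes are given as two families, not as a named score: "Using focused pain-relevant or adaptive measures as outcomes with effect size". The effects, in pooled-SD units, are "of 1, 2, 3, and 4, a regression model with treatment, age and block as effects", and the sentence ends with "an overall 0.05 significance level, 20 participants per group yields an 0.80 statistical power".

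Table 2 has six focused pain-relevant instruments and eight adaptive or emotional ones. That makes 14, or 13 if the Adverse Childhood Experience scale is left out as a history measure that training cannot change. The Outcome Measures paragraph draws the net wider. The measures for testing the hypotheses "include focused pain-relevant symptom measures, adaptive functions measures, neurocognitive measures, and PACE, as listed in Table 2". With the three neurocognitive batteries this makes 16–17 named instruments, before the walking time.

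Statistical Analyses goes below instrument level: "Multivariate analyses for the responses of scales/subscales weighted scores", with covariates that include "pre-treatment scores, will use the Generalized Linear Mixed Modeling (GLMM) approach". It also allows t-tests and/or non-parametric tests, and marks no analysis as the decisive one. Hypothesis (a) in Overview and Background joins several domains in one sentence: GRIT "will be associated with reduced chronic pain and related symptoms of insomnia, anxiety, depression, improved emotional functions, and improved neurocognitive functions". It does not say whether one, some or all must be shown.

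**The concern.** An overall significance level has meaning only relative to a stated set of tests and a stated rule for success. The plan supplies neither. The 0.05 could apply to each measure singly, to any one success, or to all of them together, and these have different error rates and different power.

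This matters because the study is presented as more than descriptive: "This pilot study seeks to test the efficacy of a resilience skills training intervention". The hypotheses are directional, and Future Plans says a further funding proposal will follow. Without a named primary test, the choice among 13 or more scales, their subscales and two or three types of analysis could be made after the results are seen. A reader would then take one significant result as carrying the stated 0.05.

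The power half of the sentence has a defect of its own. One power figure cannot describe four effect sizes at a fixed sample size.

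**Working it through.** **Inputs from the plan:** 20 per arm, 1:1 allocation, level 0.05, effects of 1, 2, 3 and 4 SD, a model with treatment, age and block, and 13–14 measures. **Assumptions:** two-sided testing (not stated), correlations between measures, pre–post correlation and intraclass correlation. The documents give none of these.

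**1. The plan's own power figure.** For one test on independent participants, the standard error of the difference in SD units is √(2/20) = 0.316, so the noncentrality is d/0.316 = 3.162·d. The critical t on 38 df is 2.024.

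- d = 1: noncentrality 3.162, power 0.869. On 36 df (age and block fitted) it is 0.868. One-sided on 36 df it is 0.927.
- d = 2: noncentrality 6.325, power above 0.999. It is higher still at 3 and 4 SD.
- Solving for power 0.80 gives d = 0.909 (38 df) or 0.910 (36 df).

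So 0.80 is not reproduced at any listed effect.

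**2. Chance of at least one false positive.** Suppose there is no true effect, each measure is tested at unadjusted two-sided 0.05, and any significant one may be claimed. For independent measures this is 1 − 0.95^m: 1 − 0.95^13 = 0.487 and 1 − 0.95^14 = 0.512. For a common correlation ρ it is

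1 − ∫ φ(x) · [Φ((1.96 − √ρ·x)/√(1−ρ)) − Φ((−1.96 − √ρ·x)/√(1−ρ))]^m dx.

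| Assumed ρ | 13 measures | 14 measures |
|---|---|---|
| 0 | 0.49 | 0.51 |
| 0.5 | 0.33 | 0.35 |
| 0.7 | 0.24 | 0.25 |
| 0.9 | 0.14 | 0.14 |

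Simulated t-tests with 20 per arm and 13 measures agree: 0.487, 0.342, 0.245 and 0.140.

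**3. Conditions behind any restated power.**

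- *Training in groups.* GRIT is delivered in groups of 5–12. Take 10 per group and an intraclass correlation (ICC) in the trained arm only. The variance of the difference is then [1 + (1 + 9·ICC)]/20. At ICC 0.05 it is 2.45/20 = 0.1225, noncentrality 1/√0.1225 = 2.857, power 0.80 at 1 SD. At ICC 0.10 it is 2.90/20 = 0.145, noncentrality 2.626, power 0.73. Neither figure uses baseline adjustment or deducts degrees of freedom for the small number of groups.
- *Baseline adjustment.* With pre–post correlation r, the effect acts as d/√(1−r²) on 37 df. Power of 0.80 then falls at 0.79 SD (r = 0.5) or 0.65 SD (r = 0.7), for independent participants.
- *Permitted minimum.* The plan allows 20 participants in total. At 10 per arm the noncentrality is 1/√(2/10) = 2.236 and power at 1 SD is 0.56.

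**The case against.** The strongest reply is that *overall* directly follows the description of a regression model and that the outcome families are joined by *or*. It may therefore mean one model, one outcome and 0.05, in which case power at 1 SD is 0.87 and the stated 0.80 is met. This stands as a possible reading, so a reader should not infer that the plan claims family-wise control over 13–14 measures and fails to deliver it. But that reading covers one outcome, and none is named. Nor does the word *multivariate* help: what is described is a covariate-adjusted mixed model for scales and subscales, with no joint or composite test.

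A split of 0.025 to each of two families would give 0.79 at 1 SD, close to the stated figure. No split is stated, and it would not cover several measures within a family.

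Two other strong readings go too far. One is that the false-positive rate is about one half. That needs independent measures, which is implausible for overlapping pain, sleep, mood and stress scales, and a claim-any-one rule that the plan never states. The other is that the trial is underpowered. Bonferroni over 13 measures would give per-measure power of 0.54 at 1 SD, but the plan does not say that it uses Bonferroni, and at 2 SD the figure is 0.999.

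Pilot status also counts. The plan calls the study a pilot that gathers preliminary data, so formal control over every measure is not needed. Having stated an overall level and a power, however, the plan should say what they apply to.

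**Conclusion.** The point holds in limited form and should be fixed. In the text available, the overall 0.05 has no defined scope. The inflation, from 0.49 with independent measures down to 0.14 at correlation 0.9, is conditional on any unadjusted significant measure being claimable, and the correlations are assumptions. Even at 0.9 the rate is nearly three times 0.05. The count of 13 is conservative as a number of instruments, because subscales and the neurocognitive tests add more. It is not an established number of planned tests, because the weighted scores are not defined.

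The power mismatch is separate and needs no assumption about correlations between measures. With two-sided testing and independent participants, 20 per arm gives 0.87 at 1 SD and above 0.999 from 2 SD, and 0.80 belongs to about 0.91 SD. It shows that the sentence is wrong as written, not that 20 per arm is too few.

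The statement that nothing is named covers only the text available. Appendix 1, which the plan describes as a list of outcome measures, and some removed parts could not be checked.

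**What to change.** Before any unblinded analysis:

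1. Name one primary outcome. The domain and score are the sponsor's choice; a pain score would fit the study title and the first-listed hypothesis.
2. Test it once, ImT versus DeT at the first post-test, with the baseline-adjusted model at two-sided 0.05.
3. Label all other measures and subscales secondary. Report them as estimates with 95% confidence intervals and no significance claims, or Holm-adjusted.
4. Rewrite the power sentence for that one test with one effect size and its power. Drop the word *overall* and the list of four effects.
5. State the conditions with it: 20 per arm analysed, the pre–post correlation if baseline adjustment is credited, and the assumed clustering in training groups. The 0.87 at 1 SD should not be quoted without them. Say also that the permitted minimum of 10 per arm gives about 0.56 at 1 SD.

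The cost is one paragraph in Statistical Considerations and one label in Table 2. Sample size, visits and data collected do not change. The downside is that secondary results can no longer be claimed at a nominal 0.05, and hypothesis domains other than the primary have no unadjusted formal test. That is acceptable in a pilot gathering preliminary data.

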#### **5. Intervention Training**

There will be two Immediate Training ImT groups of 5-12 participants per training group and two Delayed Training DeT control groups with 5-12 participants in each group. One Immediate ImT intervention group will be trained at one time for 4 weeks with 2 biweekly sessions, followed by post-testing. During this time the Delayed DeT group waits, since only one group can be trained at one time. The Delayed DeT group will receive training after waiting 4 weeks and a first post testing session. At the end of its training, the DeT group will receive a second post-testing session.

Training sessions will be held at the Morehouse School of Medicine in the Research Wing. There will be two 90-minute training sessions per week, taking place between 4-6pm on two days out of Mondays through Thursdays. The exact days and times of the training will be set in advance for each group, and will not be accommodating of individual schedules.

Should a participant miss a scheduled training session or be unable to complete a session in full, the attendance requirements are as follows:

Participants are allowed to miss 2 out of 8 sessions. They are also given the option to make up one or both sessions. They are allowed to make up a maximum of 2 sessions. If they miss a 3rd session, they are not allowed to make it up but can stay in the study. If they miss a 4th session, they will be terminated from the study. The content of the makeup sessions will follow the content of the modules: (1) introduction to concepts (2) illustrative examples (3) applications to own life with exercises. Makeup sessions will be one-on-one with the interventionist, and will last no more than 30 minutes. Participants will be compensated for makeup sessions as they are for group training sessions they attend.

If a participant attends but cannot complete a training session, it will be considered a missed session if they leave before the half-way time point (45 minutes). In this case the above policy regarding missed sessions will apply. If they leave the training session after 45 minutes, they may complete the rest of the session as a homework assignment, since homework

assignments are practiced at the end of each session. Participants will only be compensated for incomplete sessions if they attend for at least half (45 minutes).

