## **6. Homework**

The Study Workbook (within Appendix 6) contains all assignments, practice exercises, and instructions. Each module is to be completed in two sessions of one week. Homework is assigned at the beginning of each week and to be turned in at the beginning of the next week. For each module, the homework asks participants to find examples from their lives of the main concept covered in that module, note their sensory reactions, and apply the examples to change how they experience pain and stress.

The Habit Maker Checklist tracks the application of training concepts and activities in participants' everyday life. Participants are to complete one checklist for each week.

Completion of The Study Workbook and the weekly Habit Maker Checklist questionnaire are required of all participants, and participants may be withdrawn from the study if they are not completing their homework assignments.

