## **7. Control Condition**

As previously described, the control condition is the Delayed DeT group that waits for 4 weeks while the Immediate ImT group experiences the GRIT training. At the end of the four weeks of training of ImT and waiting of DeT, both groups are post-tested. At that point the Delayed DeT group receives the GRIT training and then a second post-testing.

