## **Withdrawal Criteria**

Investigators may withdraw a subject from the study at any time for the following reasons:

- The participant has not met the training attendance or testing session scheduling requirements of the study, as outlined above
- The participant has not met the homework requirements of the study, as outlined above
- A serious adverse event occurs
- The investigator considers, for safety reasons, it is in the best interest of the individual participant or other participants that the individual participant stop participation in the study

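### Before post-test 1 the attendance and homework rules can remove only ImT participants, and nothing in the text provides a post-test 1 for those removed

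*Combined protocol and SAP*

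**What the plan says.** **Removal rules.** The footnote to Table 3 (*Subjects*), repeated in *5. Intervention Training*, says of participants who miss a fourth "session, they will be terminated from the study". *6. Homework* adds that "participants may be withdrawn from the study if they are not completing their homework assignments". *Withdrawal Criteria* lists both as grounds on which investigators may withdraw someone: "The participant has not met the training attendance or testing session scheduling requirements of the study, as outlined above" and "The participant has not met the homework requirements of the study, as outlined above".

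**The control arm.** *Intervention Training for Former Players* says: "The delayed (DeT) group wait during these 4 weeks and do not receive training". *5. Intervention Training* agrees: "During this time the Delayed DeT group waits, since only one group can be trained at one time". DeT is trained only after its first post-test.

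**Post-test 1.** *7. Control Condition* says: "At the end of the four weeks of training of ImT and waiting of DeT, both groups are post-tested". Table 5 shows the same range of N at pre-test and post-test 1. *8. Post-Testing* places the assessment after the 4-week training and times it from the last session.

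**Missing data.** *Statistical Considerations* says: "For all analyses intent-to-treat principles will be adopted for those who drop out". Post-treatment values are then to come from multiple imputation based on pre-treatment scores.

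**The concern.** The rules end participation in the study, not only in training. During the weeks before the between-arm comparison they can apply to one arm only. The protocol itself can therefore cause outcome data to be lost in ImT with no counterpart in DeT.

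The loss need not be unrelated to outcome. Under *Risks/Assessment*, a participant distressed by the group topics may have a session ended early, and incomplete sessions fall under the attendance rules. Under *5. Intervention Training*, leaving before 45 minutes counts as a miss. Poor tolerance of the training can thus lead to termination. People who stop attending may also differ in prognosis.

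Imputation supplies a modelled value for those removed, and the answer depends on how they would have scored. A post-test that was never taken cannot be recovered at analysis.

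**Working it through.** **1. Who can be removed before post-test 1.** Attendance is counted over 8 training sessions, and DeT has none until after its first post-test. *6. Homework* requires homework of all participants, but it is module work, two sessions per module per week, so it begins with training. Both rules can therefore act only on ImT before post-test 1. The interventionist role descriptions mention a 90-minute control visit; no other available text gives DeT a visit while it waits, and the wording should be reconciled. Test-scheduling failures, skipping a whole test, safety withdrawal and voluntary dropout can affect either arm and are not part of this point.

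**2. Whether those removed are tested.** *7. Control Condition*, *8. Post-Testing* and Table 5 give the general plan; none mentions a participant already removed. *10. Compensation & Reimbursement* pays for sessions attended whether or not post-testing is completed, so it foresees people leaving without one. *3. Enrollment & Tracking* lists dropouts, withdrawals and terminations separately, so a rule worded for dropouts does not clearly cover the other two.

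**3. How often (assumed rates).** The plan gives no removal rate. Its nearest figure is the allowance of up to 8 beyond 40 for attrition of all kinds: 8/48 = 16.7%, or about 4 per arm. For the attendance rule alone, take independent misses with probability p and X ~ Binomial(8, p):

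| p | P(X ≥ 4) | of 24 ImT | of 20 ImT |
|---|---|---|---|
| 0.10 | 0.005 | 0.1 | 0.1 |
| 0.20 | 0.056 | 1.4 | 1.1 |
| 0.30 | 0.194 | 4.7 | 3.9 |

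Some of these people would have left or declined testing anyway. No frequency can be given for homework withdrawal.

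**4. Size of the bias (assumed scenarios).** Let n = 24 per arm, k be the number lost from ImT, and f = k/n. Completers gain 1 SD and those lost gain b. Those lost would have scored d SD worse untreated at the same pre-score. DeT contains the same share of such people, and all of DeT is tested.

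- True intent-to-treat effect: (1 − f) + f·b
- Arm in the imputation model, or those lost excluded: 1 + f·d
- Arm omitted: (1 − f) + f·[(n − k) − k·d]/(2n − k) + f·d

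For k = 4, d = 0.5, b = 0, f = 4/24 = 0.167:

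- truth = 0.833
- with arm = 1 + 0.083 = 1.083, bias +0.25
- arm omitted = 0.833 + 0.167 × (20 − 2)/44 + 0.083 = 0.985, bias +0.15

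Bias in SD for k = 2 and k = 4 (positive favours training):

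| Those lost | Arm in model, or excluded | Arm omitted |
|---|---|---|
| (a) d = 0, b = 0 | +0.08, +0.17 | +0.04, +0.08 |
| (b) d = 0, b = 1 | 0, 0 | −0.04, −0.09 |
| (c) d = 0.5, b = 0 | +0.13, +0.25 | +0.08, +0.15 |
| (d) d = −0.5, b = 1 | −0.04, −0.08 | −0.08, −0.17 |

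Simulation of 8 cases (3,000 trials each, 5 imputations, pre-post correlation 0.6, ANCOVA on arm and pre-score) agreed with the imputation formulas within 0.005 SD.

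**5. Scale.** The standard error is √(2/24) = 0.289 SD unadjusted. Adjusted for pre-score at an assumed correlation of 0.6 it is 0.289 × √(1 − 0.36) = 0.231 SD.

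**The case against.** The strongest reply is that the plan already deals with this. Intent-to-treat covers all analyses, missing post-treatment values are imputed, and both groups are to be post-tested. The reference to completed training in *8. Post-Testing* covers untrained DeT participants too, so it may be a calendar marker and not a condition on each person. On that reading, all that is missing is a sentence saying what termination means for outcome testing. The consent pages and appendices, which were not available, might contain one.

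The second reply concerns size. Expected non-attendance is an exclusion, two sessions can be made up, a third miss is tolerated, sessions are paid and homework withdrawal is discretionary. Under the binomial model, 4 of 24 removed needs a miss rate of about 28% per session, and it would use up ImT's whole share of the attrition allowance. At 20%, f = 0.056 and the bias with arm in the model is about 0.06 SD in (a) and 0.08 SD in (c). At 10% the largest listed bias is about 0.01 SD. The scenarios also assume full DeT follow-up, and people who missed four paid sessions may decline a test visit.

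The points on size stand, and they are why the bias is called probably modest. They do not remove the asymmetry. An imputed value is not an observation, pre-scores carry no information on response to training, and the calendar reading still leaves unsaid whether a terminated participant is tested.

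**Conclusion.** The concern holds. On the available text, the attendance and homework rules can remove only ImT participants before post-test 1, and no post-test 1 is provided for them. The direction of any bias is unknown. Its size rests on assumed removal rates and on how those removed would have fared: near zero if almost nobody is removed, and up to +0.25 SD, about one standard error, in the most adverse case shown. The reading of the text is firm; the size is not. It merits correction even in a pilot, because the stated aim is to test the intervention and the results are meant to inform a further proposal.

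**What to change.** 1. **Main change.** Without altering when training ends, state that the attendance and homework rules do not end outcome assessment. Invite every randomised participant to post-test 1 on the common group schedule and analyse as randomised. Safety withdrawals and withdrawal of consent stay as written.
2. **Remaining gaps.** State that the imputation covers terminated and withdrawn participants as well as dropouts, and put randomised arm, pre-score, age and block in the imputation model. These are already terms of the planned analysis model.
3. **Optional.** Add one sensitivity analysis imputing ImT non-completers from the DeT distribution. It is not a bound. With benefit between 0 and 1 SD, the arm-based and DeT-based results enclose the truth only if those lost and those retained have the same untreated outcome. With k = 4, d = 0.5, b = 0, the DeT-based result is (1 − f) + f·d·(1 − f) = 0.90 and the arm-based result 1.08, against a truth of 0.83.
4. **Wording.** Reconcile the control-visit text in the interventionist role descriptions with the waiting control.

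**Cost.** Protocol and SAP wording, plus one $75 visit and 90 to 120 minutes of the existing blinded testers' time per person removed. For 2 to 4 people that is $150 to $300 and 3 to 8 hours (2 × 1.5 to 4 × 2). Some of those invited may decline, and the estimate will include non-adherers.
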